# 6.2.3 During treatment (visits 2-4)

See flowchart (section 6.1) for which clinical examinations are performed at each study visit. Some particular considerations follow:

- Should the patient need replenishment of study medication, it will be logistically handled by the study nurse.
- Points 6-12 from section 6.2.2 are repeated.

# 6.2.4 End of study (Visit 4)

- End of study (Week 12): Patients bring with them remaining study medication which is gathered by the study nurse for a pill count. Clinical examinations are performed as listed in section 6.1.
- Points 6-10 from section 6.2.2. are repeated.
- At the end of the study visit, consider changes in standard treatment with cholinesterase inhibitors or memantine.

# 6.3 Criteria for Patient Discontinuation

Patients may be discontinued from study treatment and assessments at any time. Discontinuation and the reason for discontinuation (withdrawn from the study) will be registered. Specific reasons for discontinuing a patient for this study are:

- Voluntary discontinuation by the patient who is at any time free to discontinue his/her participation in the study, without prejudice to further treatment.
- Any form of expression, both verbal and non-verbal, by a participant opposing participation, either before or during the study, will be respected.
- Safety reason as judged by the Principal Investigator.

 Incorrect enrollment, i.e. the patient does not meet the required inclusion/exclusion criteria for the study.

• Deterioration in the patient's condition which in the opinion of the Principal Investigator warrants study medication discontinuation (to be recorded as an AE or under Investigator Discretion).

# 6. 4 Procedures for Discontinuation

#### 6.4.1 Patient Discontinuation

Patients who are withdrawn from the study before start of treatment, will be replaced. Withdrawn patients are not followed up.

# 6.4.2 Trial Discontinuation

The whole trial may be discontinued at the discretion of the PI or the sponsor in the event of any of the following:

- Occurrence of AEs unknown to date in respect of their nature, severity and duration.
- Medical or ethical reasons affecting the continued performance of the trial.
- Difficulties in the recruitment of patients.

The sponsor and principal investigator will inform all investigators and the Ethics Committees of the termination of the trial along with the reasons for such action. If the study is terminated early on grounds of safety and Ethics Committees will be informed within 15 days.

# **7** ASSESSMENTS

The schedule of assessments is indicated in Section 6 (see section 6.1, Flow Chart).

# 7.1 Safety and Tolerability Assessments

Safety will be monitored by the assessments described below as well as the collection of AEs at every visit. Significant findings that are present prior to the signing of informed consent must be included in the relevant medical history/ current medical condition page of the e-CRF. For details on AE collection and reporting, refer to Section 8.

For the assessment schedule refer to study flow chart in Section 6.1.

# 7.2 Clinical Assessments

# 1. Medical history:

Performed by: investigator

- a. Family history of parkinsonism:
  - i. Who
  - ii. Which illness.

- b. Family history of Dementia:
  - i. Who
  - ii. Was the diagnosis certain, probable or possible
- c. Family history of cardiovascular disease
- d. Smoking history:
  - i. Active smoker, previous smoker, or never smoker?
  - ii. Years since smoking cessation (if applicable)
  - iii.

iv.

- e. Alcohol use
  - i. Average alcohol units per week (if applicable)
- f. First AD symptoms:
  - i. Which symptoms: memory, orientation, language, behavior, other (if other = free text comment).

#### 2. Vital signs:

Performed by: study nurse

- a. Blood pressure.
- b. Pulse.
- c. Temperature.

#### 3. Body metrics:

Performed by: study nurse

- a. Body weight.
- b. Height.
- c. BMI.

## 4. Physical examination:

Performed by: investigator

- a. Heart and lung auscultation.
  - i. Heart: normal / findings (free field)
- ii. Lungs: normal / findings (free field)b. Abdominal palpation: normal / findings (free field)
- c. Any other examination dictated by patient's condition/symptoms: free field.

#### 5. General neurological examination

Performed by: investigator

a. Register any findings not related to the subject's parkinsonism: free field.

#### 6. Clinical scales & registrations:

Performed by: see individual tests below

a. MoCA:

Performed by: investigator or study nurse

b. ADAS-COG

Performed by: investigator or study nurse

c. CDR:

Performed by: Investigator or study nurse

d. Trail Making Test (TMT)

Performed by: Investigator or study nurse

e. MADRS:

Performed by: investigator study nurse

f. NPI-Q:

Performed by: study nurse

g. IADL and PADL

Performed by: study nurser

h. 3-day dietary record:

Performed by: self-filled by the patient and patient's study partner

## 7.3 Routine Laboratory Tests

These will include: CRP, ALAT, ASAT, GT, bilirubin, ALP, creatinine, urea, RBC, Hb, WBC with differential, platelets, CK, FT4, TSH, B12, folic acid, homocysteine, methylmalonic acid, sodium, potassium, glucose. Women of childbearing potential will also have a pregnancy test performed.

Laboratory tests and biosampling are listed and described in detail in Appendix A.

## 7.4 Imaging studies

- 31P-MRS (CSI, multinuclear coil 15 min) will be conducted on a 3T Biograph mMR MR-PET scanner (Siemens Healthcare, Germany) to assess the intracerebral concentration of NAD, as we have done previously.
- 2. **FDG-PET** imaging will be performed on the same MR-PET scanner and in the same session, to assess the metabolic response to NR treatment, as we have previously shown. Following standard preprocessing protocols and spatial normalization, the NRRP will be assessed using using ordinal trends/canonical variates analysis (OrT/CVA), a supervised form of principal component analysis (PCA). This multivariate approach is designed to detect and quantify regional covariance patterns (i.e., metabolic networks) for which expression values (i.e., subject scores) increase or decrease with treatment in all or most of the subjects.

The MRI protocol is also summarized in Appendix B.

## 7.5 Molecular analyses

- 1) Metabolomics analyses will be performed in snap-frozen blood, PBMC, and CSF, using liquid chromatography-mass spectrometry (LC-MS) as described. Absolute metabolite concentrations will be determined using in house standards. We will assess the entire NAD-metabolome, and key-metabolites involved in the Krebs' cycle, fatty acid beta-oxidation, and methylation reactions (e.g., SAM, homocystein, folate).
- **2) Gene and protein expression.** The transcriptome will be mapped in PBMC and/or PAXgene samples by RNA-sequencing, using ribosomal depletion and sequencing at 125 bp paired-end and 100 million read pairs per sample, as we have previously described. Quantitative proteomics will be performed in PBMC, muscle and CSF, using TMT (Tandem Mass Tags) labeling and mass spectrometry (LC-MS/MS Q-Exactive HF).
- **3) Histone acetylation profiling**. As in our previous work, we will first assess quantitative changes in global histone acetylation status in PBMC and muscle, by immunoblotting with a pan-acetyl-lysin antibody. Next, acetylation levels of specific lysine residues (e.g., H3K27 and H4K16) will be assessed with targeted immunoblotting. Finally, genome-wide changes in the acetylation status of histone lysine residues found to be quantitatively altered by the treatment, will be assessed by chromatin-immunoprecipitation sequencing (ChIP-Seq).

- 4) Inflammatory cytokine concentration will be determined in CSF using ELISA as in the NADPARK trial.
- 5) DNA methylation will be mapped in PBMC and/or snap-frozen blood using the Illumina Infinium Epic Chip.
- 6) Neurotransmitter levels. Monoamine levels will be determined in the CSF using HPLC-MS.
- **7) Gut microbiome.** Using fecal samples, we will assess the microbiota profile (i.e., estimates of composition and abundance) by metagenomics, and function by microbial metabolomics. Metagenomics analyses will comprise 16S-rRNA sequencing-based count of operational taxonomic units (OTUs), Illumina NovaSeq short-read sequencing, and long-read sequencing by MinION technology. For microbial metabolomics, feces will be analysed for short-chained fatty acids (SCFA) and, if feasible, NAD-related metabolites.

## **8 SAFETY MONITORING AND REPORTING**

The investigator is responsible for the detection and documentation of events meeting the criteria and definition of an adverse event (AE) or serious adverse event (SAE). Each patient will be instructed to contact the investigator immediately should they manifest any signs or symptoms they perceive as serious.

The methods for collection of safety data are described below.

#### 8.1 Definitions

#### 8.1.1 Adverse Event (AE)

An AE is any untoward medical occurrence in a patient administered a pharmaceutical product and which does not necessarily have a causal relationship with this treatment.

An adverse event (AE) can therefore be any unfavorable and unintended sign (including an abnormal laboratory finding), symptom, or disease temporally associated with the use of an investigational product, whether or not related to the investigational product.

The term AE is used to include both serious and non-serious AEs.

If an abnormal laboratory value/vital sign is associated with clinical signs and symptoms, the sign/symptom should be reported as an AE and the associated laboratory result/vital sign should be considered as additional information that must be collected on the relevant CRF.

# Only intensity 2 and 3 is registered as AE in eCRF, see section 8.3. An AE has to interfere with everyday life to be of intensity 2 or 3.

## 8.2.1 Serious Adverse Event (SAE)

Any untoward medical occurrence that at any dose:

- Results in death
- Is immediately life-threatening
- Requires in-patient hospitalization or prolongation of existing hospitalization
- Results in persistent or significant disability or incapacity
- Is a congenital abnormality or birth defect
- Is an important medical event that may jeopardize the subject or may require medical intervention to prevent one of the outcomes listed above.

Medical and scientific judgment is to be exercised in deciding on the seriousness of a case. Important medical events may not be immediately life-threatening or result in death or hospitalization, but may jeopardize the subject or may require intervention to prevent one of the listed outcomes in the definitions above. In such situations, or in doubtful cases, the case should be considered as serious. Hospitalization for administrative

reasons (for observation or social reasons) is allowed at the investigator's discretion and will not qualify as serious unless there is an associated adverse event warranting hospitalization.

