**KG7** – **Determine whether NR therapy alters methylation metabolism and characterize any dose dependence of such an effect.** In theory, NAD replenishment via NR administration could decrease/deplete the cellular methylation capacity. NR boosts the NAD-metabolome, leading to increased production of the degradation product nicotinamide (NAM), which is eliminated via methylation to MeNAM, Me-2-PY, and Me-4-PY, and excreted in the urine. Synthesis of Me-Nam requires the methyl-donor S-adenosylmethionine (SAM). This, in turn, could limit SAM availability for other essential methylation reactions, such as DNA and histone methylation, and neurotransmitter synthesis, including dopamine. Thus, in theory, NR would cause an increased consumption of SAM, limiting methylation reactions and generating higher levels of homocystein. Such a phenomenon would be a particular concern for the ~60% of the population that carries MTHFR variants that reduce the efficiency of methylation. The NADPARK study showed no change in serum homocystein levels, or any other evidence of methylation depletion associated with NR 1000 mg daily. It is, however, unknown whether such effects may occur with higher NR doses.

**KG8** – **Determine how orally ingested NR interacts with the microbiome in AD**. Current evidence suggests that the gut microbiome may be involved in the pathogenesis of AD and that individuals with AD host a different microbiome composition compared to neurologically healthy individuals. It is possible that NR therapy may beneficially affect the gut microbiome in AD restoring normal patterns. On the other hand, it is also possible that variation in the gut microbiome may affect local metabolism of NR and absorption in the bloodstream. These effects have not been studied.

**KG9** – **Determine whether NR therapy influences gastrointestinal (GI) motility in AD**. GI dysmotility due to dysfunction and degeneration of both central and local neuronal populations controlling GI motility occurs in AD. It is possible that NR may improve the function of these neurons and preserve them against the neurodegenerative process.

To address these pertinent questions, we will conduct N-DOSE AD, a multi-center randomized double-blinded placebo-controlled trial to assess the optimal biological dose for NR in AD.

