#### **Assessment of Intensity**

The investigator will make an assessment of intensity for each AE and SAE reported during the study and assign it to 1 of the following categories:

- 1 Mild: An event that is easily tolerated by the participant, causing minimal discomfort and not interfering with everyday activities.
- 2 Moderate: An event that causes sufficient discomfort to interfere with normal everyday activities.
- 3 Severe: An event that prevents normal everyday activities. An AE that is assessed as severe should not be confused with an SAE. Severe is a category utilized for rating the intensity of an event; and both AEs and SAEs can be assessed as severe.

The Causal relationship of the event to the study medication will be assessed as one of the following:

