5.5 Sample size

Our primary null hypothesis (H_0) is that the NR-induced increases in cerebral NAD levels (measured by ^{31}P -MRS), or NRRP expression (measured by FDG-PET) are not dose-responsive. The alternative hypothesis (H_A) is that at least one of these measures will be dose responsive. In the NADPARK study, all three measures showed a highly significant increase in the group receiving 1000 mg NR ($n = 15$) compared to the placebo group ($n = 15$). In the NADPARK study⁹, treatment with 1000mg of NR led to an increase in cerebral NAD-levels by a factor of 1.27 from baseline in the treatment group, whereas the change in the placebo group was negligible at -0.43%. Under the H_A , we assume that cerebral NAD levels will increase in a linear fashion in the 2000 mg NR and 3000 mg NR groups, respectively. Based on these assumptions and given a type I error rate of 5% ($\alpha = 0.05$) and a type II error rate of 10% ($\beta = 0.1$, power = 90%), we estimated that a sample size of 30 individuals will be required in the dose escalation group. Accounting for drop-out and statistical safety margin, we estimate that the study requires 40 subjects in this group.

For the secondary outcomes, we assume that the metabolomic analyses will have sufficient power, since they produced very large effect sizes and highly significant results in the NADPARK study with 15 individuals per group.

6 Safety Analyses

General safety evaluations will be based on the incidence, intensity, and type of AEs, and clinically significant changes in the patient's physical examination findings, vital signs, and clinical laboratory results. Only AE grade 2 and above will be recorded. Safety variables will be tabulated and presented for all patients in the safety set.

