6.1.2 Sensitivity Analyses

Sensitivity analysis of data will be performed by comparing the results of analysis with the SAS and PPS populations. If there is a notable difference this will be commented upon.

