6.2 Clinical Laboratory Parameters

Safety clinical laboratory parameters were collected and assessed, both to be used to identify adverse events and for exploratory analyses. Clinical laboratory parameters will be summarised by treatment group and visit.

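### The AE rules keep symptom-free laboratory abnormalities and mild events out of the safety endpoint, leave mild-rated SAEs without a planned table row, and repeat the AE tables in the per-protocol set

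*Protocol*

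**What the plan says.** **Definition.** Protocol 8.1.1 defines an AE as "any unfavorable and unintended sign (including an abnormal laboratory finding), symptom, or disease" that is temporally associated with the product, and says the term covers serious and non-serious events. If a laboratory abnormality comes with symptoms, the symptom is reported as the AE and the laboratory value is supporting information. SAP 6.2 says laboratory parameters were collected "both to be used to identify adverse events and for exploratory analyses".

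**Registration threshold.** The statement that closes protocol 8.1.1 reads "Only intensity 2 and 3 is registered as AE in eCRF, see section 8.3", followed by "An AE has to interfere with everyday life to be of intensity 2 or 3". Protocol 8.3 repeats the threshold, and the opening paragraph of SAP section 6 agrees: "Only AE grade 2 and above will be recorded". Intensity 1 (mild) is described as "causing minimal discomfort and not interfering with everyday activities".

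**SAEs.** Protocol 8.3 has intensity rated for SAEs as well as AEs and gives a mild stroke as an example of an event that is serious without being severe. Protocol 8.4.1 requires every SAE on the SAE pages of the e-CRF, with no intensity threshold.

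**Analysis.** The safety endpoint (protocol section 2) is the number and severity of AEs across treatment groups and dose levels. SAP 6.1.1 tabulates AEs in the safety set as moderate or severe. SAP 6.1.2 adds a sensitivity analysis "comparing the results of analysis with the SAS and PPS populations". SAP 6.2 summarises laboratory values by group and visit.

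**Toxicity of interest.** Protocol 1.1.3 (KG7) raises methyl-donor depletion with higher homocysteine. It reports no such change at 1000 mg daily and adds: "It is, however, unknown whether such effects may occur with higher NR doses".

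**The concern.** The definition and the threshold cannot both govern the AE count. A raised liver enzyme or homocysteine value without symptoms meets the definition but, by construction, cannot reach intensity 2.

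This matters because protocol 1.1.3 makes freedom from toxicity a condition of the optimal biological dose, and the only endpoint listed under safety is the AE count. The adverse effect that the protocol itself flags as open above 1000 mg would show first as a laboratory value. The safety objective also covers tolerability, yet the lowest of three severity levels is never collected. An empty AE table at 3000 mg could then be read as evidence of no toxicity when it speaks only to events that disturbed daily life.

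Two tabulation questions follow. It is unclear where a mild-rated SAE would appear, and unclear what an AE table restricted to patients who completed treatment with good adherence can show.

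**Working it through.** The plan states no AE rate or safety sample size, so there is no figure to reproduce. The passages are compared first; the arithmetic after that is illustrative, and its rates are assumptions.

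**1. Routes into the AE count**
- Laboratory abnormality with a moderate or severe symptom: enters through the symptom (protocol 8.1.1).
- Laboratory abnormality without symptoms: an AE by definition, but without interference in daily life it cannot be intensity 2 or 3, so it is not registered. If it met an SAE criterion it would reach the SAE pages.
- Mild symptom: intensity 1, not registered.
- Mild-rated SAE: recorded under protocol 8.4.1. However, the threshold in 8.1.1 states no SAE exception, and SAP 6.1.1 has neither a mild category nor an SAE table, so the event has no planned row.

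**2. Where laboratory toxicity is reported instead**
- SAP section 6 refers to clinically significant laboratory changes but gives no criterion for them.
- SAP 6.2 plans summaries by group and visit.
- Protocol 10.4 compares abnormal results between treatment and placebo descriptively.
- Homocysteine is measured at weeks 0, 4, 8 and 12 (protocol 6.1, 7.3 and Appendix A section 2). It is missing from the list in Appendix A 2.1.1 that is presented as covering all safety parameters. Liver enzymes are on that list.

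**3. What a zero in the AE table would mean**
The one-sided 95% upper bound with no events is 1 − 0.05^(1/n).
- n = 20 (placebo, or the DS-group alone): 13.9%
- n = 40 (DE-group at 2000 or 3000 mg): 7.2%
- n = 60 (1000 mg, 20 DS plus 40 DE): 4.9%

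Under the threshold these bounds apply to moderate or severe events only.

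**4. Share of events registered (assumed rates)**
Take n = 40 at 3000 mg, AE risk p and mild share m. Expected events are 40p, expected registered events are 40p(1 − m), and P(at least one registered) = 1 − [1 − p(1 − m)]^40.

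| p | m | Expected | Registered | P(at least one registered) |
|---|---|---|---|---|
| 10% | 50% | 4 | 2.0 | 0.871 |
| 10% | 90% | 4 | 0.4 | 0.331 |
| 20% | 50% | 8 | 4.0 | 0.985 |
| 20% | 70% | 8 | 2.4 | 0.916 |
| 20% | 90% | 8 | 0.8 | 0.554 |
| 30% | 90% | 12 | 1.2 | 0.704 |

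**5. Per-protocol repeat (assumed numbers)**
SAP 3.4.2 and 3.5 exclude from the PPS patients who discontinue before 84 ± 7 days or whose adherence is below 80%. Suppose 6 of 40 DE patients have a registered AE and s of them stop because of it. The safety-set rate is 6/40 = 15.0% throughout. The PPS rate is (6 − s)/(40 − s):
- s = 0: 6/40 = 15.0%
- s = 3: 3/37 = 8.1%
- s = 6: 0/34 = 0%

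The number of patients with an AE in the PPS can never exceed the number in the safety set. The percentage falls whenever patients with AEs are over-represented among those excluded. It could rise slightly if only unaffected patients were excluded: with 4 such exclusions, 6/36 = 16.7%.

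**The case against.** The strongest reply is that the AE count is only one part of the safety evaluation. SAP section 6 also rests on laboratory results, vital signs and physical findings. Protocol 10.5 lists routine blood tests as a dependent variable, with mean changes between and within arms. A symptom-free enzyme rise would therefore be reported, though not as an AE. The threshold is applied consistently in both documents and looks deliberate. Intolerance that affects drug-taking would still show in compliance by group (SAP 3.4.1) and in recorded reasons for discontinuation (protocol 6.3). All of this stands. It reduces the problem to one of definition and presentation, but does not remove the conflict between protocol 8.1.1 and SAP 6.2 on one side and the threshold on the other.

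Four stronger readings are tempting, and the documents do not support them.
- *A mild-rated SAE would go unrecorded.* Protocol 8.4.1 requires every SAE on the SAE pages, and 8.5 has SAEs discussed in the study report. Only the tabulation is missing.
- *Homocysteine gets no dose comparison.* Protocol 7.5 includes it among the methylation metabolites, and SAP 4.4 plans model-based comparisons for one-carbon metabolism. These are exploratory, their method may change, and they are not safety analyses, but they exist.
- *The PPS repeat hides harm.* SAP 6.1.1 fixes the safety set for the AE analysis, so early stoppers stay in the main table; the PPS result appears only as a comparison beside it.
- *A quarter of the DE-group is expected to leave the PPS.* The step from 30 to 40 in protocol 10.1 covers drop-out and a safety margin together and gives no split.

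**Conclusion.** The concern holds in limited form. The AE definition, the registration threshold and the stated use of laboratory values conflict. As a result, symptom-free laboratory abnormalities (unless they are SAEs) and all mild non-serious events lie outside the stated safety endpoint. Laboratory values are reported, but without a criterion for clinical significance, and it is uncertain whether homocysteine counts as a safety parameter. A mild-rated SAE is captured but has no planned row. The PPS repeat conditions on completing and adhering to treatment, both of which may be consequences of an AE. Where AEs cause the exclusions it understates harm, and it adds nothing to the safety-set table.

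The size cannot be fixed from the documents; the event risks, mild shares and stopping numbers above are assumptions. The textual conflict depends on none of them. The primary endpoint is untouched. The point should be settled before the safety conclusion is written, because the optimal-dose definition relies on it.

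**What to change.** - **Reconcile** protocol 8.1.1 and 8.3 with SAP section 6, 6.1.1 and 6.2, so that it is clear whether a laboratory abnormality can be an AE, and that the intensity threshold does not apply to SAEs.
- **SAP 6.1.1:** add a table of all SAEs at any intensity, by group and dose level.
- **SAP 6.2:** have the sponsor state its criterion for a clinically significant abnormality. Tabulate such abnormalities by group and dose level, with shift tables from baseline, for the values already collected. Name liver enzymes and homocysteine, and bring the list in Appendix A 2.1.1 into line. Present these tables with the AE endpoint when judging toxicity for the optimal dose.
- **SAP 6.1.2:** delete the PPS repeat of the AE tables.
- **Report:** state that mild AEs were not registered, so the AE table covers moderate and severe events only.

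Starting to register mild events now is not advised. The protocol synopsis estimates the last patient completed at 30.06.2025, and SAP 6.2 speaks of laboratory collection in the past tense. A late change would mix two ascertainment rules and leave a mild row incomplete for earlier patients.

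The cost is some extra tabulation and short text edits, with no new visits, samples or data.
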